Title: In vivo characterization of the non-genomic effects of T3 on endothelial and cardiovascular function

NCT #: NCT03098433

Document date: 01/19/2017

Document Type: Protocol and Statistical Analysis Plan

In vivo characterization of the non-genomic effects of T3 on endothelial and cardiovascular function

Study protocol

Research Description

Hypothyroidism is a common condition caused by failure of the thyroid gland or as a result of thyroid surgery for benign or malignant lesions. Hypothyroidism is treated by administering levothyroxine (LT4) a synthetic inactive form of the thyroid hormone. This drug is then metabolized by the organism into its active form, T3.

Several lines of evidence indicate that LT4 alone may not be sufficient in assuring adequate tissue levels of T3 and some studies suggest that the addition of liothyronine (LT3) the synthetic form of T3 to LT4 can improve the symptoms and signs associated with hypothyroidism. LT3 has a short half life and it is usually administered in two-three doses daily. There is also evidence supporting the hypothesis that T3 exerts rapid, "non genomic" effects, particularly on the vessels. If this is the case a tight regulation of the LT3 dose to maintain the serum concentration of T3 becomes of primary importance.

To assess the non genomic effect of LT3 we will perform a proof-of-concept, double blind randomized crossover study in twenty healthy volunteers aimed to measure the acute cardiovascular and energy expenditure changes following a single equimolar dose of LT3 or LT4.

Specific aims or goals.

Aim 1: To compare the effects of a single dose of 0.7mcg/kg in liquid formulation (equivalent to a dose of 50 mcg in a 70 Kg individual) of LT3 to an equimolar 0.86 mcg/kg single dose of LT4 in liquid formulation, and to placebo on cardiovascular system. We will record the following parameters: heart rate, blood pressure, cardiac output, flow-mediated dilation.

Aim 2: To compare the effects of a single dose of 0.7mcg/kg of LT3 in liquid formulation to an equimolar single dose of LT4 in liquid formulation, and to placebo on the energy metabolism and substrate utilization. We will record the following parameters: energy expenditure by whole room indirect calorimeter, respiratory quotient, skin and core temperature.

Aim 3: To measure the changes in circulating thyroid hormone following a single dose of 0.7mcg/kg of LT3 in liquid formulation to an equimolar single dose of LT4 in liquid formulation, and to placebo. We will record at multiple time points the following parameters: free T3, free T4, TSH.

Background and significance.

Thyroid hormone (TH) affects development, growth and function on the majority of tissues of the organism and the specificity of the signaling is assured by a complex, multilevel system that assures time- and tissue-specificity of the hormonal signal relatively independent from the circulating levels(1). Among the various systems, the peripheral metabolism of pro-hormone T4, the main product of the thyroid, into the hormonally active T3 plays a crucial role in assuring the tissue-specific delivery of the hormonal signal(2). Two enzymes, type-1 (D1) and type-2 (D2) deiodinase, convert T4 into T3. Of note, D1 is thought to be responsible for a substantial fraction of circulating T3(3). Hypothyroidism is an extremely prevalent condition affecting approximately up to 10% of the adult population and is

associated with dyslipidemia, cognitive impairment, hypertension, and increased cardio-vascular morbidity and mortality(4, 5). Autoimmune thyroid disease (AITD) is the most common etiology of hypothyroidism in the US and it is characterized over a period of years by progressive loss of functional parenchyma. Since the thyrotroph is exquisitely sensitive to minimal changes in circulating TH, a compensatory increase in Thyroid Stimulating Hormone (TSH) secretion occurs while levels of TH are still well within the range of normality. This is illustrated by the classical linear-logarithmic relationship between free T4 and TSH(6). As the disease progresses, while the circulating T4 decrease to frankly pathologic levels, T3 tends to remain within normal range until extreme hypothyroidism ensues(7, 8). Similar conditions are observed in iodine insufficiency, and in experimental models of perturbation of the thyroid homeostasis(9). In aggregate, these observations suggest that multiple homeostatic mechanisms have developed to protect the circulating, and by extension the intracellular levels, of T3. Of interest, some of the hormonal actions of T3 are exerted via a rapid non-genomic pathway, which appears to play an important role in some of the cardiovascular effects of TH(10, 11). The therapy of hypothyroidism consists in administration of LT4, which in turn is converted into the active metabolite T3 in the peripheral tissues by D1 and D2. The therapeutic goal is a TSH within normal range, indicating the achievement of euthyroidism at the level of the thyrotroph on the assumption that a state of pituitary euthyroidism equates to adequate T3 concentration in all the tissue targets of the hormonal action(12). This assumption has been challenged by clinical observations(13), clinical trials(14), and mechanistic studies(15). The results of clinical studies aimed to measure the effects of TH replacement on “hard” endpoints (i.e. mortality and cardiovascular events) have been marginal or disappointing, particularly in subclinical hypothyroidism and in the elderly(16). This is surprising since the cross-sectional data provide compelling evidence of the association between hypothyroidism and indexes of cardiovascular risk. Collectively these data question the utility of TH replacement, its therapeutic goals, the target population who could benefit from the intervention, and the modality of the treatment, and indeed there is active discussion on this very topic within the thyroidologist community(17). The attempt to provide a more “physiologic” form of therapy has led to the experimentation of combinationLT3 /LT4 regimens(13, 18-29), or to the use of thyroid extracts(30). Furthermore, some observations suggest that carriers of a common polymorphism of the D2 gene (Thr92Ala) (31)may benefit from combination therapy, suggesting a pharmacogenomics component in the therapeutic response(14, 32). This information indicate that the current therapy for hypothyroidism is costly and suboptimal, and there is need for a formal characterization of the pathophysiologic state of hypothyroidism during replacement treatment.

This project challenges the established notion that LT4 generates identical biological effects on the pituitary and on the end-organ tissues, and pituitary euthyroidism (*i.e.* a normal TSH) is pharmacodynamically equivalent to production of TH from the normal thyroid gland. We will interrogate the clinical relevance of non-genomic effects of TH by assessing the short-term effects of a single-dose of LT3 on endothelial and cardiovascular function. This translational project will provide important information on the need (or lack thereof) of maintaining stable circulating levels of T3. In this clinical protocol, we chose as primary endpoints measurable and clinically relevant indices of TH action, which in turn could be used in the future as outcomes for large intervention studies. Specifically, beside measurements of circulating TH, we will assess energy expenditure(33, 34) and endothelial (35, 36)and cardiovascular function(37). The results of the proposed experiments will shed light on the interaction between the pathophysiologic state of hypothyroidism and administration of therapy, providing new

insights on the clinical rationale and utility of targeting the circulating levels of T3. Collectively, these studies will expand the knowledge base necessary to design a rationale treatment of hypothyroidism.

Study design.

Proof-of-concept, randomized double blind cross-over study in healthy volunteers. Twenty adult healthy volunteers will be invited to participate in the study.

A) Screening visit. Age $>18<45$ year, BMI $>20<30$ kg/m² TSH $>0.5<5.0$ mIU/mL and no evidence of thyroid autoimmunity by history or anti-thyroid peroxidase (TPO) antibodies measurement. Exclusion criteria will be: pregnancy; hypothyroidism or autoimmune thyroid disease by history or presence of anti TPO antibodies; use of prescription drugs; diabetes mellitus; dyslipidemia; coronary artery disease; hypertension (systolic blood pressure > 140 mm/Hg, and/or diastolic blood pressure > 90 mm/Hg); anemia; renal insufficiency; liver disease or ALT >2.5 x the upper laboratory reference limit; psychiatric conditions; and current tobacco use. During the screening visit, the following procedures will be performed: informed consent, history and physical examination, EKG, CBC, glucose, creatinine, ALT, hCG (in females), TSH, freeT4, TPO, and genomic DNA.

B) Study visit #1-3. Study participants will be evaluated in the morning after an overnight fast during three consecutive outpatient visits, with at least a 24-hour interval between. Upon arrival to the Clinical Research Service Unit (CRSU) and abbreviated history and physical examination with recording of anthropometrics will be obtained; an i.v. cannula will be inserted in the left arm. Study volunteers will be fitted with electrodes for EKG Holter recording, and a cuff on the third finger of the right hand to record blood pressure and heart rate, cardiac output, systemic vascular resistance and endothelial function. An echocardiogram will be recorded at the beginning and at the end of each study session. Study volunteers will then enter in the whole room ("Flex room") a 4' x 8' x 7' indirect calorimeter with a temperature set at 24°C and rest on a bed. The Flex room has a window and a TV monitor, and is connected to the nursing station via an interphone system. An i.v. port is located on the door of the Flex room allowing drawing of samples without compromising the recording of energy expenditure. After 40 minutes (time 0'), study volunteers will receive either 0.7mcg/kg (equivalent to a dose of 50 mcg in a 70 Kg individual) of LT3 to an equimolar 0.86 mcg/kg single dose of LT4, and to placebo in liquid form. The doses were chosen to be within the usual therapeutic range prescribed in preparation for radioiodine ablation. Blood samples will be obtained at the following time points: 0', 60' 120' 180' 240' for total and free T3, total and free T4, TSH and 500 μ l aliquots of serum TSH will be recorded at times 0' and 240' of each Study visit. Energy expenditure and respiratory quotient will be recorded throughout the duration of the stay in the Flex room. The first 20 minute of the recording will be discarded to allow for equilibration. At the end of the session the i.v. cannula will be removed, vital signs recorded and the volunteer will be discharged provided with a coupon for a meal in the hospital cafeteria. The same procedures will be repeated in the identical order and timing for the other formulations.

Justification for the sample size:

The primary analysis will be performed by two-tailed paired t-test with an 0.05 α error as a threshold for statistical significance on the assumption that LT3 administration, compared to LT4 will result in a 30% increase in FMD, corresponding to 0.75 SD. Using this experimental conditions and assumptions, a 20 volunteers will provide 88% power to detect a significant difference, while assuming a 20% drop-out rate the power will be 80%.

List the study inclusion criteria:

Healthy volunteers, both sexes

Age range 18-45 year

Body Mass Index range 20- 30 kg/m²

Ability to provide informed consent to the participation in the study

List the study inclusion criteria:

Abnormal TSH (>0.5<5.0 mIU/mL)

Thyroid disease or autoimmunity by history or anti-thyroid peroxidase (TPO) antibodies.

Pregnancy or lactation

Chronic use of prescription drugs

Diabetes mellitus (by history or fasting glucose >126 mg/dl)

Dyslipidemia (total cholesterol >240 mg/dl)

Hypertension (by history or screening systolic blood pressure > 140 mm/Hg, and/or diastolic blood pressure > 90 mm/Hg)

Cardiac arrhythmia (by history or screening EKG)

Anemia (Hb<13.3 g/dl M, 12.0 g/dl F)

Renal insufficiency by history or estimated creatinine clearance ≤ 60 mL/min/1.73m² BSA.

Liver disease or transaminases >2.5 x the upper laboratory reference limit.

Current tobacco use.

Criteria for withdrawing an individual participant from the study:

Volunteers may withdraw from the study at any time. The investigators can withdraw any volunteer at any time from the study if medically necessary.

Medical reasons for withdraw from the study:

- 1) Tachycardia (heart rate greater than 100/min)
- 2) Anxiety
- 3) Development of hypertension (systolic >160 mmHg, diastolic > 90 mmHg) following administration of the study drug
- 4) Development of hypotension (systolic <90 mmHg, diastolic < 60 mmHg) following administration of the study drug

Adverse events mitigation:

All AEs and SAEs will be followed until resolution, until the condition stabilizes, until the event is otherwise explained, whichever occurs first. All AEs and SAEs documented at a previous visit/contact

and designated as ongoing, will be reviewed at subsequent visits/contacts, where the designation may remain ongoing. The investigator will ensure that the follow-up includes any supplemental investigations as may be indicated to elucidate the nature and/or causality of the SAE. This may include additional laboratory tests or investigations, histopathological examinations, or consultation with other health care professionals. SAEs that are ongoing at the time of the subjects final study visit/contact will be documented as ongoing.

DSMP.

The PI will be responsible for data and safety monitoring during the study. A physician not affiliated with the research proposal will serve as independent compliance officer and will review quarterly compliance with inclusion/exclusion criteria, gender and minority, adverse events. The results of the review will be reported to the PI and the IRB.

1. Yen PM 2001 Physiological and molecular basis of thyroid hormone action. *Physiological reviews* **81**:1097-1142.
5. Rodondi N, den Elzen WP, Bauer DC, Cappola AR, Razvi S, Walsh JP, Asvold BO, Iervasi G, Imaizumi M, Collet TH, Bremner A, Maisonneuve P, Sgarbi JA, Khaw KT, Vanderpump MP, Newman AB, Cornuz J, Franklyn JA, Westendorp RG, Vittinghoff E, Gussekloo J, Thyroid Studies C 2010 Subclinical hypothyroidism and the risk of coronary heart disease and mortality. *JAMA : the journal of the American Medical Association* **304**:1365-1374.

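### The paired t-test named for this randomised three-visit crossover puts visit-to-visit change into its error and so loses power; fix a period-adjusted LT3–LT4 difference on six near-equal sequences as primary, and treat carry-over as a possible bias for sensitivity analysis

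*Combined protocol and SAP*

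**What the plan says.** The Study design section of the combined protocol and SAP describes a "Proof-of-concept, randomized double blind cross-over study in healthy volunteers". Under B) Study visit #1-3, each volunteer receives LT3, LT4 and placebo at "three consecutive outpatient visits, with at least a 24-hour interval between". The section ends: "The same procedures will be repeated in the identical order and timing for the other formulations". No treatment sequences and no rule for balancing them are given, and no reason is stated for the 24-hour minimum.

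Under Justification for the sample size, the document's only analysis is given as follows: "The primary analysis will be performed by two-tailed paired t-test with an 0.05 α error as a threshold for statistical significance". The contrast is LT3 against LT4 on FMD, with an assumed difference of 0.75 SD. The power is put at 88% with 20 volunteers, and the section adds: "assuming a 20% drop-out rate the power will be 80" per cent. No period, sequence or preceding-treatment term is mentioned.

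On persistence of effect, the Research Description says "LT3 has a short half life and it is usually administered in two-three doses daily" and calls LT4 inactive. Background and significance says LT4 is converted to active T3. No duration of effect on FMD is given for either drug.

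**The concern.** Two things other than treatment can move FMD between visits in a crossover, and a paired t-test has a term for neither.

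- **Period.** FMD may change from visit 1 to visit 3 for everyone, for example through familiarity with the procedure. The change then differs between volunteers according to the visits at which they had LT3 and LT4, and the test treats that spread as random error. A term for visit removes it.
- **Carry-over.** If part of one drug's effect remains at the next visit, and the amount differs between LT3 and LT4, the LT3–LT4 difference shifts even with perfectly balanced sequences. A term for visit does not remove this.

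Power is planned at 80% with 16 completers, so nothing is in reserve for a period effect. The sequence list decides how far chance imbalance can move the estimate.

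**Working it through.** **Inputs.** From the sample-size section: effect 0.75 SD, two-sided α = 0.05, n = 20, or 16 after 20% drop-out (20 × 0.8). From the design section: three treatments, three visits, randomised order. The unit throughout is the SD of the within-person LT3–LT4 difference, because the stated power reproduces on that reading. The documents give no size for a period or carry-over effect, so those sizes are assumptions, shown as a range.

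**1. The plan's own figure.** Paired t-test power comes from the non-central t with n − 1 df and non-centrality 0.75√n.
- n = 20: 0.75 × 4.472 = 3.354, 19 df, power 88.9% (stated 88%).
- n = 16: 0.75 × 4 = 3.000, 15 df, power 80.1% (stated 80%).

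Both reproduce, with no period or carry-over effect in the model.

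**2. Period effect in the paired t-test.** Suppose FMD changes by δ per visit. A volunteer's difference is then 0.75 + δ × (visit of LT3 − visit of LT4) + error. Over the six orders the visit gap is −1, +1, −1, +1, −2, +2. Its mean is 0 and its mean square is (1+1+1+1+4+4)/6 = 2. So the average estimate is unchanged, while the variance the test sees rises from 1 to about 1 + 2δ².

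The power and type I error below are simulated and averaged over all 15 near-equal allocations to six sequences.

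| δ per visit | 1 + 2δ² | Power n=20 / n=16 | Type I error |
|---|---|---|---|
| 0 | 1.000 | 89% / 80% | 5% |
| 0.25 | 1.125 | 86% / 76% | about 4% |
| 0.375 | 1.281 | 82% / 71% | about 3% |
| 0.5 | 1.500 | 77% / 64% | about 2% |

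Type I error falls because balancing keeps the drift out of the mean while the test still counts it in the standard error. With unrestricted random order, type I error stays at about 5%, and power at n = 20 is about 85% at δ = 0.25 and 74% at δ = 0.5.

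**3. Shift in a single trial.** Twenty is not a multiple of six, so the most even split is 4,4,3,3,3,3. If the two extra volunteers have gaps of 2 and 1 in the same direction, the mean gap is 3/20 = 0.15 visits. At δ = 0.5 that moves the estimate by 0.15 × 0.5 = 0.075 SD. With unrestricted randomisation the mean gap is up to 0.6 visits in 95% of allocations, so δ = 0.375 can move the estimate by up to 0.6 × 0.375 ≈ 0.22 SD.

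**4. Period-adjusted LT3–LT4 difference.** Regress each volunteer's difference on an intercept (the treatment effect) and two columns, for visits 2 and 3, coded +1 if LT3 was given at that visit, −1 if LT4 was, and 0 otherwise. This leaves n − 3 df (17 and 13). The design matrix inflates the variance by a factor of at most 1.01 at n = 20 and 1.03 at n = 16 over the near-equal splits. Power is about 88% at n = 20 and 78–79% at n = 16, whatever δ is. Placebo data are not used, so the placebo variance cannot affect type I error.

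**5. Three-visit subject-treatment-period model.** Power is 90% / 82% on 36 / 28 df. It pools variance across treatments: type I error is about 7% if the placebo visit has half the variance of the others, and about 3% if it has double.

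**6. Carry-over.** Take carry-over after placebo as zero. LT4 immediately precedes LT3 in 2 of the 6 sequences, and LT3 immediately precedes LT4 in 2 of 6. The LT3–LT4 difference therefore shifts by (LT4 carry-over − LT3 carry-over)/3. Equal carry-over cancels. For illustration, 0.375 SD from one drug gives 0.375/3 = 0.125, so the estimate is 0.625 (LT3 only) or 0.875 (LT4 only) instead of 0.75. Adding period terms leaves those averages unchanged. Adding preceding-treatment terms to the three-visit model restores 0.75, at about 83% / 73% power (34 / 26 df).

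**The case against.** The case for leaving the plan alone is reasonable. The trial is randomised, the stated power reproduces, and this is a 20-person proof-of-concept study. The assumed drifts are not small: 0.5 SD per visit is 1.0 SD from first visit to last, more than the 0.75 SD treatment effect. Carry-over of 0.375 SD would mean half the assumed effect persisting after a single dose and at least 24 hours, when the protocol itself says LT3 has a short half-life. The three-visit model often used instead brings its own exposure to unequal variances.

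Most of this stands, and it rules out several stronger readings that a reader might infer.

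- *That visit order biases the test or produces false positives.* Under randomised order it does neither on average; with balanced sequences the test becomes conservative. A positive result would not be undermined by drift.
- *That everyone receives the treatments in the same order.* The sentence about identical order concerns the study procedures, and the trial is described as randomised.
- *That the visit interval leaves residual drug effect.* The documents point both ways and give no duration, so carry-over is neither shown nor excluded.
- *That the stated power is wrong.* It is right for the case it assumes.

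What remains is that randomisation does not protect against lost power, chance imbalance among 20 people, or unequal carry-over. The first two can be dealt with by wording alone.

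**Conclusion.** The point holds as one of efficiency and pre-specification, and it should be fixed. The named test is valid under randomised order, but its power is as stated only if FMD does not change between visits. Under an assumed linear change of 0.25 to 0.5 SD per visit with near-equal sequences, power falls to about 86–77% with 20 volunteers and 76–64% with 16. A period-adjusted difference holds about 88% and 78–79%.

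Carry-over is a separate, unaddressed possibility. With six balanced sequences it would shift the result by one third of the difference in carry-over between the drugs, and no period term would correct that.

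These figures rest on 0.75 SD being in units of the paired difference, on a linear drift, on near-equal use of all six sequences, and on first-order additive carry-over. The sizes of drift and carry-over are assumptions; the documents support none in particular.

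**What to change.** 1. **Sequences.** List all six orders of LT3, LT4 and placebo, and allocate volunteers as evenly as possible (4,4,3,3,3,3).
2. **Primary analysis.** In place of the paired t-test, name one analysis in advance: the within-person LT3-minus-LT4 difference in FMD, adjusted for period. State that it removes period effects, not carry-over. The three-visit subject-treatment-period model may be listed as supporting, with its equal-variance assumption stated. The choice between them must not depend on the data.
3. **Sensitivity analysis.** Pre-specify one: the three-visit model with preceding-treatment terms added. Also describe the 0' free T3, free T4 and TSH, already collected, by preceding treatment. Neither should trigger a change of primary analysis.

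**Cost.** This needs SAP wording and a sequence list, with no new visits, volunteers or measurements. If there is no period effect, the primary analysis gives up about 1 to 2 points of power: about 88% against 88.9% at n = 20, and 78–79% against 80.1% at n = 16. The latter is just under the stated 80%, and the sample-size section should say so. The sensitivity analysis has about 83% / 73% power and also assumes equal variances, so it should not be primary. No visit interval is proposed here.

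### Cheap improvement: the LT3–LT4 paired t-test in this three-visit crossover has no period term; balanced orders and a period-adjusted test would protect power at little or no cost

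*Combined protocol and SAP*

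**What the plan says.** The Study design section describes a "Proof-of-concept, randomized double blind cross-over study in healthy volunteers". Under Study visit #1-3, volunteers attend "during three consecutive outpatient visits, with at least a 24-hour interval between", and receive LT3, LT4 and placebo. Aim 1 compares LT3 with LT4 "and to placebo on cardiovascular system".

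Under Justification for the sample size, one analysis is given: "The primary analysis will be performed by two-tailed paired t-test with an 0.05 α error as a threshold for statistical significance". It assumes that "LT3 administration, compared to LT4 will result in a 30% increase in FMD, corresponding to 0.75 SD", and concludes that "a 20 volunteers will provide 88% power to detect a significant difference", or 80% power after 20% drop-out.

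The documents do not give:
- a list of treatment orders or a method for balancing them;
- a period or sequence term;
- the size of any visit effect on FMD;
- the time of the FMD reading relative to dosing, or whether change from pre-dose is analysed. The finger cuff that records "cardiac output, systemic vascular resistance and endothelial function" is fitted before the 40-minute pre-dose stay in the calorimeter room.

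The statement that procedures are repeated in the same order and timing concerns the procedures within a visit, not the order of treatments.

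**The concern.** With three treatments there are six possible orders. Each volunteer's LT3–LT4 difference is the treatment effect plus the difference between the two visits at which those treatments fell. If FMD drifts across visits, or the first visit differs from the rest, that visit difference varies between volunteers according to order. A plain paired t-test counts this predictable variation as random error.

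What is at stake is power. The plan allows for 80% after drop-out, which leaves no margin. A period term removes the variation without new volunteers or measurements.

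**Working it through.** **Inputs from the sample-size section.** Two-sided α = 0.05; effect 0.75 SD; n = 20; 20% drop-out, so 20 × 0.8 = 16. The section does not say which SD is meant. The stated power fits only the SD of the paired difference, so that is the unit below. As 30% of FMD is 0.75 SD, a shift of 0.25 SD is 10% of FMD and 0.5 SD is 20%.

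**1. The plan's own power.** Noncentral t with noncentrality 0.75√n and n − 1 df:
- n = 20: 0.75 × 4.472 = 3.354, 19 df, power 88.9% (stated 88%).
- n = 16: 0.75 × 4 = 3.000, 15 df, power 80.1% (stated 80%).

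Both reproduce.

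**2. How a shift enters.** Write volunteer i's difference as dᵢ = τ + (shift at the LT3 visit − shift at the LT4 visit) + eᵢ, with Var(eᵢ) = 1. Over the six orders in equal numbers, the mean squared visit difference is:
- linear 0.25 per visit: (4 × 0.25² + 2 × 0.5²)/6 = 0.125;
- first-visit step of 0.5: (4 × 0.5² + 2 × 0)/6 = 0.167;
- linear 0.5 per visit: (4 × 0.5² + 2 × 1²)/6 = 0.5.

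The error variance that the t-test sees rises from 1 to about 1.125, 1.167 and 1.5. With balanced orders the shift cancels from the mean difference, so the estimate is unbiased and the test becomes conservative: at linear 0.5 and n = 20 the type I error is 1.5–1.8%.

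**3. Power under assumed shifts.** For the paired t-test with balanced orders, power was integrated numerically, with a normal numerator and a noncentral chi-square error on n − 1 df whose noncentrality is the sum of squared visit differences. The last column averages over random losses of four from the balanced list of 20.

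| Assumed shift (SD of paired difference) | Paired t, n = 20 balanced | Paired t, four of 20 lost at random |
|---|---|---|
| None | 88.9% | 80.1% |
| Linear 0.25 per visit | 86% | 76% |
| First-visit step 0.5 | 85–86% | 74–75% |
| Linear 0.5 per visit | 76–78% | 63–64% |

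**4. Period-adjusted regression.** Regress dᵢ on an intercept and two period-difference indicators (n − 3 df), and test the intercept. An additive shift does not affect its power.
- n = 20, balanced: noncentrality 3.354, 17 df, 88.5%. Cost with no shift: 88.9 − 88.5 = 0.4 point.
- Four lost at random: mean 78.0%. Mean cost with no shift: 80.1 − 78.0 = about 2 points. The worst 5% of resulting designs fall to 75.8% or lower.
- After that loss, the paired t-test has 78.9% at linear 0.15 and 77.6% at linear 0.20, so the regression gains only above about 0.2 SD per visit.
- Simple randomisation without balancing, n = 20: about 84.6%.

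**5. Model on all three visits (subject, period, treatment).** If variances and correlations are equal across treatments, residual df = 3n − n − 2 − 2 = 2n − 4.
- n = 20, balanced: noncentrality 3.354, 36 df, 90.4%.
- Four lost at random: 28 df, mean 82.0%.
- Simple randomisation, n = 20: 88.7%.

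These figures also do not depend on an additive shift. Power under unequal variances or correlations was not calculated.

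**The case against.** **Nothing is wrong with the plan.** This stands. A reader might infer that omitting the period term biases the LT3–LT4 estimate, inflates the type I error or invalidates the stated power. The documents do not support that. The order is randomised, so a visit shift has no expected effect on the difference; the test is conservative under balanced orders; and the power calculation reproduces.

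**The benefit rests on an unknown.** This also stands. No visit effect is given, and fasting morning visits at a fixed room temperature with repeated procedures limit some sources of drift. Linear 0.5 SD per visit is 40% of FMD from first to third visit, more than the assumed drug effect, so the double-digit loss is an extreme case. For small shifts the simple regression gains nothing.

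**It may be moot.** If FMD is change from a pre-dose value in the same visit, an additive visit shift cancels. An early cuff fitting makes that possible, but the documents do not say that it is done.

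**Adjustment can itself cost power.** True of the regression on differences, mainly after drop-out or without balanced orders. It does not hold for period adjustment in general: under equal variances and correlations, the three-visit model has more power than the planned test even with no shift.

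**Conclusion.** A low-cost improvement, to consider. The planned test is valid and its 88% and 80% are right when visits do not differ. Under moderate assumed shifts (linear 0.25 SD per visit, or a first-visit step of 0.5 SD), the loss is about 3–4 points at n = 20 and about 4–6 points after random loss of four, each measured against the paired t-test with no shift. Only a large drift costs more than 10 points.

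The result rests on additive shifts of assumed size, on 0.75 SD being the SD of the paired difference, and on FMD not being analysed as within-visit change. The 90% and 82% for the three-visit model also need equal variances and correlations across treatments. A reader might take the short interval between visits to mean that the period term would also handle carryover. It would not, and nothing here shows whether carryover occurs.

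**What to change.** 1. Build the allocation list from mirrored pairs of orders: LT3 and LT4 swapped, placebo in the same position. For 20 volunteers, use three blocks of all six orders (18) plus one mirrored pair (2). LT3 and LT4 then occur equally often at each visit.
2. Make the primary test the LT3–LT4 contrast on FMD adjusted for period, two-sided 0.05, preferably from a model of all three visits with subject, period and treatment. The same model also supplies the placebo comparisons in Aim 1.
3. If equal variances and correlations across treatments are not acceptable, prespecify the regression of the LT3–LT4 difference on the two period-difference indicators (17 df with 20 pairs), and only with balanced orders.
4. State when FMD is measured and whether the endpoint is a post-dose value or change from a same-visit pre-dose value. If it is change, the planned paired t-test can stay.

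The cost is an allocation list and some SAP wording, with no new data or volunteers. The statistical price is either the equal-variance assumption or two degrees of freedom. For the regression with no shift, the latter means 0.4 point at n = 20 and about 2 points on average after random loss of four, with a worse tail.
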